### 1.2 Exploratory Objectives

The exploratory objectives are:

- To describe the effectiveness of ablation with the ThermoCool ST catheter relative to ThermoCool STSF for the treatment of persistent AF using the propensity score balanced data.

- To describe the effectiveness of ablation with the ThermoCool STSF catheter for the treatment of ischemic VT using the unadjusted data.
- To describe the safety of ablation with the ThermoCool STSF catheter for the treatment of overall VT on a composite safety endpoint using the unadjusted data. The overall VT population will be identified using the same criteria as ischemic VT except removing the requirement of prior MI.
- To describe the safety of ablation with the ThermoCool STSF catheter in a subgroup that excludes non-ischemic cardiomyopathy patients using a composite safety endpoint in the ischemic VT population using the unadjusted data.
- Explore the sensitivity of the safety results for persistent AF to hospital bed size. Remove hospital bed size as a balancing variable for patients with persistent AF in the Mayo data source. Perform the balanced outcome analysis with this modification in Mayo and recalculate an average difference (all Mercy hospital bed sizes were above the prespecified bed size cut point of 500 so this covariate was not included in the Mercy propensity score model).
- Explore the sensitivity of the safety results for ischemic VT by performing an outcome analysis comparing the ThermoCool STSF group to the ST group using the balanced data.
- Perform exploratory subgroup analyses among patients with a prior prescription of class I or III AAD before the index ablation procedure for the persistent AF population using propensity score balanced data.

Determinations about comparative effectiveness and safety of these exploratory objectives will not be based on hypothesis tests, rather examination of point and confidence interval estimates within each group and differences.

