#### 4. Analytic Methods to Meet the Primary and Exploratory Objectives

##### 4.1. Treatment

In the persistent AF analysis the subject device group is the ThermoCool ST catheter and the comparison group is the ThermoCool STSF catheter. In the ischemic VT analysis the subject device group is the ThermoCool STSF catheter.

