##### 4.2 Covariates

For persistent AF an extensive list of covariates was considered. In 4.2.1 the original list is displayed. However, in some instances there was evidence of a positivity violation (i.e., there are

no observations in one of the device arms for at least one of the levels of a nominal covariate) or a value for a covariate was present for all patients in the data. All modifications to the original covariates for these reasons are described as notes to the tables provided in the Appendix.

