#### 4.4 Missing Data

Missing data on the outcomes can occur due to loss to follow-up. These patients will be censored at the time at which follow-up terminated. Missing data on the treatment variable is addressed in the study inclusion criteria. For missing covariate information an informative missing data approach is adopted, such that for nominal variables we create a separate level to indicate a missing value, and for continuous variables the mean is imputed and indicator variable for missing values on that variable is created [2]. The variables with levels representing missing data and missing data indicator variables were included in the propensity score model unless there was a positivity violation (i.e., there are no observations in one of the device arms with missing data on a particular covariate).

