#### 4.6.2 Method for Covariate Balancing

We considered several PS methods to maximize balance [7] (see appendix, tables 1-4). For ischemic VT, none of the methods considered adequately balanced the data, therefore a comparative design was not pursued in favor of single arm design using a performance goal [8]. For persistent AF a singular method that minimizes imbalance across the two data sources was selected, average treatment effect on the treated weights [9] with weight trimming/winsorizing [10]. Specifically, patients receiving the subject device receive a weight of 1 and those receiving the comparator device (c) receive a weight based on the odds,  $w_i = \frac{\hat{e}_i}{1-\hat{e}_i}$ , where  $\hat{e}_i$  = estimated propensity score for patient  $i = 1, \dots, n_c$ . Furthermore, patient weights in the comparator group only are trimmed/winsorized at the 95th percentile of the weight distribution (i.e., all weights with value above the 95th percentile are set equal to the 95th percentile).

When used with logistic regression to estimate the propensity score, weight trimming has been shown to reduce bias in estimating the treatment effect when the model is mis-specified due to non-linear and non-additive effects, as well as to increase precision of the estimated treatment effects [10]. Use of untrimmed ATT weights has been shown unbiased in simulation studies in estimating the risk difference using survival data [11].

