| 0.20          |  |  | 9    | 9    | 14   | 14   | 10   | 9    |
| Mean ASD      |  |  | 0.37 | 0.60 | 0.45 | 0.45 | 0.33 | 0.31 |

Note: When using stratification, covariate balance for a particular covariate is the average balance across strata ( $k = 1, \dots, 5; K = 5$ ), calculated using  $\sum_{k=1}^K w_{(k)} \hat{d}_{(k)}$ , where  $w_{(k)} = \frac{n_{s(k)}}{n_s}$  and  $n_s$  is the number of patients with the subject device. Elixhauser not included as a covariate in the propensity score model because for STSF there were 0 instances of patients with scores  $\leq 3$ .

Table 4. Ischemic VT: Mayo Balance Results

| Variable             | Value     | STSF       | ST         | Crude | Strata | Untrimmed | Trimmed
99 | Trimmed
95 | Trimmed
90 |
|----------------------|-----------|------------|------------|-------|--------|-----------|---------------|---------------|---------------|
| Age (cat)            |           |            |            | 0.229 | 1.581  | 0.828     | 0.589         | 0.108         | 0.124         |
|                      | <65       | 11 (31.4%) | 31 (36.9%) |       |        |           |               |               |               |
|                      | 65-74     | 13 (37.1%) | 35 (41.7%) |       |        |           |               |               |               |
|                      | >=75      | 11 (31.4%) | 18 (21.4%) |       |        |           |               |               |               |
| Sex                  |           |            |            | 0.085 | 0.542  | 0.537     | 0.508         | 0.141         | 0.123         |
|                      | Male      | 31 (88.6%) | 72 (85.7%) |       |        |           |               |               |               |
|                      | Female    | 4 (11.4%)  | 12 (14.3%) |       |        |           |               |               |               |
| Race                 |           |            |            | 0.010 | 0.315  | 0.315     | 0.288         | 0.036         | 0.051         |
|                      | White     | 33 (94.3%) | 79 (94.0%) |       |        |           |               |               |               |
|                      | Non-White | 2 (5.7%)   | 5 (6.0%)   |       |        |           |               |               |               |
| Elixhauser Index     |           |            |            | 0.151 | 1.886  | 1.642     | 0.949         | 0.078         | 0.059         |

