|                      | <=3       | 1 (2.9%)   | 5 (6.0%)   |       |        |           |               |               |               |
|                      | >3        | 34 (97.1%) | 79 (94.0%) |       |        |           |               |               |               |
| Index Year           |           |            |            | 1.793 | 0.458  | 0.462     | 0.332         | 1.019         | 1.066         |
|                      | 2014-18   | 5 (14.3%)  | 68 (81.0%) |       |        |           |               |               |               |
|                      | 2019-21   | 30 (85.7%) | 16 (19.0%) |       |        |           |               |               |               |
| BMI                  |           | 32.0 (7.0) | 30.6 (6.7) | 0.194 | 0.046  | 0.622     | 0.397         | 0.010         | 0.025         |
| Hx:CHF               |           | 33 (94.3%) | 74 (88.1%) | 0.220 | 1.263  | 1.373     | 0.745         | 0.040         | 0.051         |
| Hx:Stroke            |           | 7 (20.0%)  | 26 (31.0%) | 0.253 | 0.714  | 0.116     | 0.287         | 0.134         | 0.124         |
| Hx:AFib              |           | 21 (60.0%) | 43 (51.2%) | 0.178 | 1.402  | 0.455     | 0.001         | 0.007         | 0.006         |
| Hx:HTN               |           | 30 (85.7%) | 73 (86.9%) | 0.035 | 1.672  | 1.332     | 0.716         | 0.023         | 0.019         |
| Hx:Diabetes          |           | 9 (25.7%)  | 24 (28.6%) | 0.064 | 0.809  | 0.814     | 0.759         | 0.186         | 0.181         |
| Hx:Anemia            |           | 5 (14.3%)  | 15 (17.9%) | 0.097 | 0.584  | 0.564     | 0.501         | 0.116         | 0.101         |
| Hx:Valve replacement |           | 4 (11.4%)  | 10 (11.9%) | 0.015 | 0.509  | 0.461     | 0.421         | 0.044         | 0.039         |
| Hx:VT Admission      |           | 26 (74.3%) | 57 (67.9%) | 0.142 | 1.473  | 0.840     | 0.355         | 0.099         | 0.128         |

|                        |            |            |            |       |       |       |       |       |
|------------------------|------------|------------|------------|-------|-------|-------|-------|-------|
| Tx: ICD Pacemaker      | 31 (88.6%) | 58 (69.0%) | 0.492      | 0.757 | 0.899 | 0.865 | 0.421 | 0.399 |
| Tx: AAD Class I or III | 25 (71.4%) | 66 (78.6%) | 0.166      | 0.726 | 0.636 | 0.568 | 0.009 | 0.003 |
| Tx: Anticoagulants     | 21 (60.0%) | 40 (47.6%) | 0.250      | 1.374 | 0.387 | 0.060 | 0.021 | 0.006 |

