| Operator Volume        |            |            | 0.444      | 1.577 | 1.037 | 0.526 | 0.278 | 0.283 |
|                        | <10        | 16 (45.7%) | 21 (25.0%) |       |       |       |       |       |
|                        | >=10       | 19 (54.3%) | 63 (75.0%) |       |       |       |       |       |

---

Number ASDs >

|          |      |      |      |      |      |      |
|----------|------|------|------|------|------|------|
| 0.20     | 8    | 17   | 18   | 17   | 4    | 4    |
| Mean ASD | 0.27 | 0.98 | 0.72 | 0.49 | 0.16 | 0.17 |

Note: When using stratification, covariate balance for a particular covariate is the average balance across strata ( $k = 1, \dots, 5; K = 5$ ), calculated using  $\sum_{k=1}^K w_{(k)} \hat{d}_{(k)}$ , where  $w_{(k)} = \frac{n_{s(k)}}{n_s}$  and  $n_s$  is the number of patients with the subject device. A missing indicator for BMI was not included as a covariate in the propensity score model from the propensity score model because STSF had 0 instances.

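### Exploratory ischemic VT comparison: the Mercy model drops the Elixhauser index instead of restricting the ST group, and the Table 4 balance summaries do not match the rows printed

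*SAP*

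**What the plan says.** SAP 1.2 keeps an exploratory sensitivity analysis for ischemic VT, "comparing the ThermoCool STSF group to the ST group using the balanced data". Section 4.1 fixes the direction: "In the ischemic VT analysis the subject device group is the ThermoCool STSF catheter". The only weighting that the SAP specifies in detail is in 4.6.2, for persistent AF, where "patients receiving the subject device receive a weight of 1 and those receiving the comparator device (c) receive a weight based on the odds".

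Section 4.2 counts as a positivity violation any case with "no observations in one of the device arms for at least one of the levels of a nominal covariate", without regard to which arm is empty. Section 4.4 treats missing-data levels alike: they enter the model "unless there was a positivity violation (i.e., there are no observations in one of the device arms with missing data on a particular covariate".

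The Appendix shows what was done in the ischemic VT data. At Mercy (note to Table 3), "Elixhauser not included as a covariate in the propensity score model because for STSF there were 0 instances of patients with scores" of 3 or less. At Mayo (note to Table 4), "A missing indicator for BMI was not included as a covariate in the propensity score model", because STSF had no such patients. Each table ends with the number of ASDs above 0.20 and the mean ASD for six columns: crude, stratified, untrimmed weights, and weights trimmed at the 99th, 95th and 90th percentiles.

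**The concern.** Positivity has a direction when the target is the treated group. The analysis needs ST patients wherever there are STSF patients, but not the reverse. A level with ST patients and no STSF patients calls for leaving those ST patients out of the reference group. Removing the covariate keeps them in at whatever weight their other characteristics give them.

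At Mercy this means that 35 STSF patients, all scoring above 3, are compared with an ST group that may include patients of lower comorbidity, with no adjustment for the index. Since Elixhauser has no row in Table 3, a reader also cannot see how large the difference is.

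The second matter is documentary. The Appendix tables are the evidence offered for the balance achieved, so their summary rows should follow from the rows above them. In Table 4 they do not.

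**Working it through.** **Inputs.** Mercy ischemic VT: 35 STSF, 23 ST. Mayo: 35 STSF, 84 ST (Table 1 of Section 3). ASD formula for binary covariates from 4.6.3. Printed ASDs from Appendix Tables 3 and 4.

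**Step 1: Table 3 reproduces.** Its 16 printed rows, leaving out NA entries, give:

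| | Crude | Strata | Untrimmed | Trim 99 | Trim 95 | Trim 90 |
|---|---|---|---|---|---|---|
| ASDs > 0.20, from rows | 9 | 9 | 14 | 14 | 10 | 9 |
| ASDs > 0.20, printed | 9 | 9 | 14 | 14 | 10 | 9 |
| Mean, from rows | 0.371 | 0.600 | 0.450 | 0.450 | 0.325 | 0.307 |
| Mean, printed | 0.37 | 0.60 | 0.45 | 0.45 | 0.33 | 0.31 |

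The 13 two-level crude ASDs also reproduce from the printed counts to three decimals.

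**Step 2: weight of an ST patient at a level absent from STSF.** At that level the propensity to receive STSF is e = 0, so the ATT weight is e/(1 − e) = 0. Restricting ST to scores above 3 does the same directly, and the ASD of the dichotomised index is then 0 by construction.

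**Step 3: size of the omitted imbalance.** With an STSF share of 0 and an ST share q = k/23, the 4.6.3 formula becomes ASD = q / √(q(1 − q)/2) = √(2q/(1 − q)) = √(2k/(23 − k)).

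- k = 1: √(2/22) = 0.302
- k = 2: √(4/21) = 0.436
- k = 6: √(12/17) = 0.840

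Any k of at least 1 exceeds 0.20, so the crude tally moves from 9 of 16 to 10 of 17. The crude column sums to 5.937, so its mean becomes (5.937 + 0.302)/17 = 0.367 for k = 1 and (5.937 + 0.436)/17 = 0.375 for k = 2, against 0.371 now.

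For a weighted column, q is the weighted ST share. The ASD exceeds 0.20 only if 2q/(1 − q) > 0.04, that is q > 0.04/2.04 = 1.96%. The weights are not shown, so this cannot be settled.

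**Step 4: Table 4 does not reproduce.** Its 18 printed rows give:

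| | Crude | Strata | Untrimmed | Trim 99 | Trim 95 | Trim 90 |
|---|---|---|---|---|---|---|
| ASDs > 0.20, from rows | 7 | 17 | 17 | 16 | 3 | 3 |
| ASDs > 0.20, printed | 8 | 17 | 18 | 17 | 4 | 4 |
| Mean, from rows | 0.268 | 0.983 | 0.740 | 0.493 | 0.154 | 0.155 |
| Mean, printed | 0.27 | 0.98 | 0.72 | 0.49 | 0.16 | 0.17 |

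The untrimmed column shows the conflict at a glance: 18 above 0.20 would need every printed row, but Hx:Stroke is 0.116.

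**Step 5: one extra row would explain it.** Take 19 rows, with the extra one NA under Strata. For each other column, the missing ASD is 19 × the printed mean (± 0.005) minus the column sum. The trimmed-95 count also requires a value above 0.20. This gives:

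- Crude (sum 4.818): 0.22 to 0.41
- Untrimmed (13.320): 0.27 to 0.46
- Trimmed 99 (8.867): 0.35 to 0.54
- Trimmed 95 (2.770): 0.20 to 0.37
- Trimmed 90 (2.788): 0.35 to 0.54

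A BMI-missing row with 0 of 35 STSF and j of 84 ST has crude ASD √(2j/(84 − j)), which is 0.221 for j = 2 and 0.392 for j = 6. Any j from 2 to 6 fits the crude column.

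**The case against.** **Only an exploratory contrast is touched.** This stands. The primary ischemic VT test is single-arm on unadjusted data (1.1, 4.7.4), and its 57% power does not involve the propensity model. A reader might infer that the decision to abandon the comparative design is in doubt. It is not: an extra poorly balanced Mercy row would support that decision, and 3 rather than 4 at Mayo would not reverse it. Mercy already has 9 to 14 of 16 covariates above 0.20 in the weighted columns, with ICD/pacemaker at 0.915 to 1.108. Mayo index year is 1.019 at trimmed 95. Restricting ST will not by itself balance Mercy.

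**Leaving the index in would break the logistic fit.** That is a fair reason not to keep it as it stands, because its coefficient would diverge. But the limit of that fit is weight zero for the ST patients concerned, which is the restriction, not the omission.

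**The ATT rule is written for persistent AF.** True, and its use here is inferred. If ST were the target instead, ST patients scoring 3 or less would have no STSF counterpart, and restriction would again be the remedy.

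**The Mayo omission follows a stated rule.** Section 4.4 provides for mean imputation and for leaving out the indicator when one arm has none. Excluding Mayo ST patients with missing BMI would be a preference, not a correction.

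**Heart failure is in Table 4 but not in Table 3.** One might conclude that the Mercy model lacks a required covariate. The SAP shows no covariate list for ischemic VT, so this is at most a question of documentation.

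**A Table 4 row may have been lost when the PDF was read.** This cannot be ruled out. It would turn the mismatch into a missing row rather than a wrong tally.

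**Conclusion.** The point holds for the exploratory STSF-versus-ST comparison. Omitting Elixhauser at Mercy treats as a positivity violation something that is not one for an STSF target, and leaves an imbalance both unadjusted and unreported. The crude ASD is at least 0.30 if any Mercy ST patient scores 3 or less. That k is at least 1 is implied by the reason given in the note (otherwise the index would be constant in both arms), but it is not stated.

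Three stronger readings are not supported:

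- **That the Table 3 tallies are miscalculated.** They match the 16 rows exactly and are only incomplete.
- **That every Table 3 column is one count short.** This is assured for the crude column alone. The weighted columns depend on a weighted share that is not shown.
- **That the extra Table 4 row is known to be 5 of 84 ST patients with missing BMI.** The printed figures fit one unprinted row, possibly that indicator, but 2 to 6 of 84 all fit the crude column.

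The mismatch between the Table 4 summaries and the rows as available does not rest on inference; only its explanation does. The printed counts are one too high in five of six columns, so they make balance look slightly worse, not better.

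**What to change.** - For the exploratory ischemic VT comparison, restrict the Mercy ST group to Elixhauser above 3 and state how many patients this removes. The index is then constant and stays out of the model for that reason. Refit the Mercy propensity model blind to outcome and report the new balance. The new ASDs need patient data and cannot be given here.
- State in 1.2 or 4.6.2 which weights and which target group this comparison uses.
- In Table 4, either print the row that was counted or correct the summaries. For the 18 rows now printed with the existing weights, these are 7/17/17/16/3/3 and means 0.27/0.98/0.74/0.49/0.15/0.15.
- Treat covariates left out of the model the same way in Tables 3 and 4: either show and count them in both, or leave them out of the tally in both, with a note.

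The cost is k fewer Mercy ST patients in a contrast without a hypothesis test, one outcome-blind rerun, and corrected table entries.
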